4.2. Exclusion Criteria

A subject will not be eligible for inclusion in this study if any of the following criteria apply:

1. PREGNANCY

Women who have a positive urine pregnancy test

2. BREAST-FEEDING

Women who are breast-feeding

3. CONCURRENT MEDICATION/ MEDICAL HISTORY

During the entire study (Screening – last subject visit):

- Subjects who have used medications or therapies that could interfere with study evaluations and have not had the proper washout period (see Section 3.2.) from these medications or therapies or are anticipated to require any concomitant intranasal medication during that period or at any time throughout the study.
- Nasal disease(s) likely to affect deposition of intranasal medication, such as chronic sinusitis, rhinitis medicamentosa, clinically significant polyposis, or clinically significant nasal structural abnormalities.
- Nasal surgery or sinus surgery within the previous year.
- Any condition that prohibits the subject from actuating nasal spray devices (severe rheumatoid arthritis; deformed hands and fingers; missing fingers).

Document Name	CCI	Protocol B_Final_Amendment 4_Clean_QA Review		
Type	Version	Document Identifier	Effective Date	
elido_clinical_doc	1.0; CURRENT; Most-Recent; Effective	090032d580d43d4b	19-May-2017 09:57:58	
Reason For Issue	Auto Issue			

- E. Clinically relevant abnormal physical findings which, in the opinion of the Investigator or sponsor's medical monitor, would interfere with the objectives of the study or that may preclude compliance with the study procedures.
- F. Uncontrolled cardiovascular, pulmonary, renal, hepatic, gastrointestinal, hematological, endocrine, metabolic, autoimmune, neurological, psychiatric or other diseases at screening that would interfere with the study in the opinion of the Investigator.
- G. Subjects with seasonal allergic rhinitis if randomization occurs during their expected allergy season or perennial allergic rhinitis.
- H. Severe COPD, persistent asthma, or recent COPD/asthma exacerbation.
- I. An inability to comprehend and satisfactorily use the measurement instruments as determined by the study sites staff on screening.
- J. Subjects with a fever $\geq 38^{\circ}\text{C}$ (100.4°F).
- K. Frequent uses of analgesics (i.e. have taken an analgesic for pain in headache and pain in muscle/joints for ≥ 1 doses per week on average over the past 6 months).

4. ALLERGY/ INTOLERANCE

- A. Known or suspected intolerance or hypersensitivity to any of the study treatments, excipients or investigational device material or to medications of similar chemical classes.
- B. Any history of drug hypersensitivity or other significant allergic diathesis that could affect study participation.
- C. Known or suspected contraindications, including history of allergy or photosensitivity to study treatment /s.

5. CLINICAL STUDY/ EXPERIMENTAL PRODUCT

- A. Participation in another clinical study (including cosmetic studies) or receipt of an investigational drug within 30 days of the screening visit or 5 half-lives of enrollment, whichever is longer.
- B. Previous participation in this study (i.e. subjects cannot be re-screened or randomized).

6. SUBSTANCE ABUSE

- A. Recent history (within the last ≤ 1 years) of alcohol or other substance abuse.
- B. Positive urine drug screen.

Document Name	CCI	Protocol B_Final_Amendment 4_Clean_QA Review		
Type	Version	Document Identifier	Effective Date	
elido_clinical_doc	1.0; CURRENT; Most-Recent; Effective	090032d580d43d4b	19-May-2017 09:57:58	
Reason For Issue	Auto Issue			

7. PERSONNEL

- A. An employee of the sponsor or the study sites or members of their immediate family.
- B. Persons directly or indirectly involved in the execution of this protocol, including employees of the contract research organization (CRO) and persons related to them.

8. DIAGNOSTIC ASSESSMENTS AND OTHER CRITERIA

- A. On nasal examination by Investigator, the presence of nasal disease likely to affect deposition of intranasal treatment or any superficial or moderate nasal mucosal erosion, nasal mucosal ulceration, or nasal septum perforation at the screening visit.
- B. Subjects with difficulty in using the nasal spray applicator.
- C. "Vulnerable" individual (as defined by the IRB e.g. incarcerated person).
- D. Any condition not identified in the protocol that in the opinion of the Investigator would confound the evaluation and interpretation of the study data or may put the subject at risk.

4.3. Screening/ Baseline Failures

Screen failures are defined as subjects who consent to participate in the study but are never subsequently randomized.

The following information is to be collected for screen failures:

- Screening number
- Date of screening
- Date of informed consent
- Age
- Race
- Ethnicity
- Gender
- Primary reason for screen failure
- Occurrence of Serious Adverse Events (SAE); adverse events that are not SAEs will be followed by the Investigator and collected only in the source data

Re-screening of subjects is not allowed in this study.

Document Name	CCI	Protocol B_Final_Amendment 4_Clean_QA Review		
Type	Version	Document Identifier	Effective Date	
elido_clinical_doc	1.0; CURRENT; Most-Recent; Effective	090032d580d43d4b	19-May-2017 09:57:58	
Reason For Issue	Auto Issue			

4.4. Women of Childbearing Potential Definition

Female subjects of non-childbearing potential must meet at least one of the following criteria:

1. Have undergone a documented hysterectomy and/or bilateral oophorectomy;
2. Have medically confirmed ovarian failure;
3. Have undergone a documented tubal ligation;
4. Have had 12 months of natural (spontaneous) amenorrhea with an appropriate clinical profile (e.g. age appropriate, history of vasomotor symptoms).

All other female subjects (including those that do not have a documented hysterectomy, tubal ligation, bilateral oophorectomy and/or ovarian failure) will be considered to be of childbearing potential.

4.5. Withdrawal/ Stopping Criteria

A subject may withdraw from the study at any time at his/her own request, or may be withdrawn at any time at the discretion of the Investigator for ethical, safety, behavioral or administrative reasons. If a subject withdraws or is withdrawn from the study, all human biological samples collected before they left will be analyzed and reported unless the subject requests otherwise. A subject may request for their human biological samples to be destroyed. In these cases, the Investigator must document this in the site study records and the samples should not be used for any further research.

The following circumstances require discontinuation of study treatment and/or premature subject withdrawal:

- Subject did not meet study criteria
- Protocol violation that may impact the outcome of the study and/or subject's safety
- Withdrawal of informed consent
- Unblinding of the subject
- Subject lost to follow-up
- Pregnancy
- Death
- Use of disallowed concomitant medications (see Section 3.2.)

If the reason for removal of a subject from the study is an AE or an abnormal laboratory test result, the principal specific event or test will be recorded on the

Document Name	CCI	Protocol B_Final_Amendment 4_Clean_QA Review		
Type	Version	Document Identifier	Effective Date	
elido_clinical_doc	1.0; CURRENT; Most-Recent; Effective	090032d580d43d4b	19-May-2017 09:57:58	
Reason For Issue	Auto Issue			

electronic case report form (CRF). If a subject is withdrawn from the study because of a product limiting AE, thorough efforts should be clearly made to document the outcome. Any AEs ongoing at the final visit will be followed up until resolved, the condition stabilizes, is otherwise explained, or the subject is lost to follow-up.

The following actions must be taken in relation to a subject who fails to attend the clinic for a required study visit:

- The site must attempt to contact the subject and re-schedule the missed visit as soon as possible.
- The site must counsel the subject on the importance of maintaining the assigned visit schedule and ascertain whether or not the subject wishes to and/or should continue in the study.
- In cases where the subject is deemed 'lost to follow up', the Investigator or designee must make every effort to regain contact with the subject (where possible, at least 2 telephone calls). The contact attempt should be documented in the subject's record.
- Should the subject continue to be unreachable, only then will he/she be considered to have withdrawn from the study with a primary reason of "Lost to Follow-up".
- All subjects will not be permitted any use of disallowed concomitant medications. The subject will be discontinued from study treatment if the subject takes more than one dose of disallowed concomitant medications. All medications, procedures and significant non-drug therapies (including physical therapy and blood transfusions) administered after the subject starts study treatment must be listed in the CRF.

4.6. Subject Replacement

Subjects who withdraw from the study post-randomization will not be replaced.

4.7. Subject and Study Completion

A subject is considered completed after completion of the 7 days of dosing and the final assessments conducted on Day 8.

The study is considered completed after all randomized subjects have either completed all study procedures or have been discontinued from the study.

The end of the study is defined as the date of the last subject's last visit.

Document Name	CCI	Protocol B_Final_Amendment 4_Clean_QA Review		
Type	Version	Document Identifier	Effective Date	
elido_clinical_doc	1.0; CURRENT; Most-Recent; Effective	090032d580d43d4b	19-May-2017 09:57:58	
Reason For Issue	Auto Issue			

5. PRODUCT INFORMATION

5.1. Study Product

The following study products will be supplied by the Clinical Supplies Department, GSKCH:

	Test Product	Reference Product
Product Name	1146A formulation (CCI carbomer 980 gel) nasal spray	Placebo (vehicle without carbomer 980) nasal spray
Product Formulation Code (MFC)	CCI	CCI
Dose	Apply dose by alternating nostrils. 3 actuations of the 1146A nasal spray formulation per nostril per dose; each actuation is 140 μ L, (equivalent to 140mg).	Apply dose by alternating nostrils. 3 actuations of placebo nasal spray per nostril per dose; each actuation is 140 μ L.
Route of Administration	Intranasal administration	Intranasal administration
Dosing Instructions	First dosing can occur any time prior to 13:00. Subject randomization will be stratified by dosing time on Day 1 by those study subjects receiving first dose of study treatment between the hours of: 8:00-11:00 and those receiving first dose of study treatment between the hours 11:01-13:00. On Day 1, subjects dosing between 8:00-11:00 will dose every 4 hours \pm 30 minutes for 4 doses and subjects dosing between 11:01-13:00 will dose every 4 hours \pm 30 minutes for 3 doses. On Days 2-7 all subjects will administer their initial	First dosing can occur any time prior to 13:00. Subject randomization will be stratified by dosing time on Day 1 by those study subjects receiving first dose of study treatment between the hours of: 8:00-11:00 and those receiving first dose of study treatment between the hours 11:01-13:00. On Day 1, subjects dosing between 8:00-11:00 will dose every 4 hours \pm 30 minutes for 4 doses and subjects dosing between 11:01-13:00 will dose every 4 hours \pm 30 minutes for 3 doses. On Days 2-7 all subjects will administer their initial

Document Name	CCI	Protocol B_Final_Amendment 4_Clean_QA Review		
Type	Version	Document Identifier	Effective Date	
elido_clinical_doc	1.0; CURRENT; Most-Recent; Effective	090032d580d43d4b	19-May-2017 09:57:58	
Reason For Issue	Auto Issue			

	
morning dose at 07:00 ±2 hours and the remaining 3 doses every 4 hours ± 30 minutes.
 
Subjects should blow their nose prior to dosing and alternate actuations to each nostril. For each actuation subjects should insert the nozzle into the nostril, fully depress the pump and inhale gently. This should be repeated in the alternate nostril until 3 actuations per nostril have been completed. Refer to Appendix 2, Subject Instructions for Use for further details.
	
morning dose at 07:00 ±2 hours and the remaining 3 doses every 4 hours ± 30 minutes.
 
Subjects should blow their nose prior to dosing and alternate actuations to each nostril. For each actuation subjects should insert the nozzle into the nostril, fully depress the pump and inhale gently. This should be repeated in the alternate nostril until 3 actuations per nostril have been completed. Refer to Appendix 2, Subject Instructions for Use for further details.

--	---	---

CCI

Both products are filled into 10 mL amber colored glass devices fitted with an Aptar Freedop M pump. The pump is made of high-density polyethylene (HDPE), low-density polyethylene (LDPE), polypropylene and stainless steel parts and is fitted into the glass device. The pump delivers a spray of 140 mcL (equivalent to 140 mg) per actuation with a precision of ±15%.

5.2. Dose Schedule

5.2.1. Instructions for use of the medical device

During the 7 days of treatment each subject will receive in total 27-28 doses (depending on Day 1 dosing time strata). Therefore, a kit containing 5 devices for the 7 days of dosing (4 as treatment and 1 as a reserve device) will be allocated to the subject. Subjects will use a device for 2 days and then start a new device.

All study treatment will be administered by the subject following the instructions for use below. The first administration will take place at the study sites under supervision of an independent study personnel (who will have no other responsibilities during the study) on a one-on-one session with the subject in a private room. Prior to the first

Document Name	CCI	Protocol B_Final_Amendment 4_Clean_QA Review		
Type	Version	Document Identifier	Effective Date	
elido_clinical_doc	1.0; CURRENT; Most-Recent; Effective	090032d580d43d4b	19-May-2017 09:57:58	
Reason For Issue	Auto Issue			

dose the independent study personnel will prime the device in the presence of the subject as they explain the priming instructions below.

Instructions for use (by an independent site personnel):

- On Day 1, subjects dosing between 8:00-11:00 will dose every 4 hours \pm 30 minutes for 4 doses and subjects dosing between 11:01-13:00 will dose every 4 hours \pm 30 minutes for 3 doses. All subjects will be instructed to administer 4 doses on Days 2-7.
- Dose for the full seven days irrespective of symptom resolution.
- Change to a new study treatment device every 2 days and prime the new device prior to the morning dose.
- Blow nose to clear nostrils prior to dosing.
- Subjects will be instructed to complete all 6 actuations (3 in each nostril) of study treatment within 2 minutes.
- To spray, hold the device with thumb at the base and nozzle between the index and ~~ring~~ MIDDLE fingers. ~~Without~~ tilting TILT the head FORWARD SLIGHTLY, insert nozzle into the nostril. Fully depress the pump rim with a firm and even stroke and inhale gently.
- Alternate actuations to each nostril
- Wipe the nozzle clean and dry after each use defined as 6 actuations.

See Appendix 2 for more details.

Priming instructions:

The device will be removed from the kit prior to using it for the first time and will be primed prior to first use as indicated below:

- Shake the device well (only prior to priming, not prior to each use).
- Point the spray tip away from you.
- Remove the protective cap and prime the pump by depressing the pump firmly 10 times. Now the pump is ready to use.

5.2.2. Dosing

Dosing administration is 3 actuations per nostril per dose, four times a day for 7 days (except for Day 1 where subjects in the 2nd strata will receive 3 doses). Subjects will be instructed to alternate nostrils after each actuation. First administration of study treatment will occur at the study site by independent site personnel supervision; first dosing can occur any time prior to 13:00.

Document Name	CCI	Protocol B_Final_Amendment 4_Clean_QA Review		
Type	Version	Document Identifier	Effective Date	
elido_clinical_doc	1.0; CURRENT; Most-Recent; Effective	090032d580d43d4b	19-May-2017 09:57:58	
Reason For Issue	Auto Issue			

Subject randomization will be stratified by dosing time on Day 1 by those study subjects receiving first dose of study treatment between the hours of: 8:00-11:00 and those receiving first dose of study treatment between the hours 11:01-13:00. On Day 1, subjects dosing between 8:00-11:00 will dose every 4 hours ± 30 minutes for 4 doses and subjects dosing between 11:01-13:00 will dose every 4 hours ± 30 minutes for 3 doses.

On Days 2-7 all subjects will administer their initial morning dose immediately following recording of their common cold symptom assessment at 07:00 ±2 hours and the remaining 3 doses every 4 hours ± 30 minutes.

Dosing times (time that first actuation is administered) and number of actuations will be recorded in subject's e-diary.

5.3. Dose Modification

No dose modification is permitted in this study.

5.4. Product Compliance

Treatment compliance is assessed by the recording of dosing times and number of actuations in the subject e-diary.

5.5. Precautions

No special precautions are necessary provided the study is carried out in accordance with this protocol.

5.6. Overdose

An overdose is a deliberate or inadvertent administration of a product at a dose higher than specified in the protocol.

Overdose is not likely to occur in this study. Limited quantities of the product will be supplied, and closely monitored by the site for each subject.

Overdose per se is not an AE. However, any clinical sequelae of an overdose should be reported as an AE (and serious adverse event [SAE], if appropriate). For reporting, follow the AE and SAE reporting instructions provided in Section 7.4.

Document Name	CCI	Protocol B_Final_Amendment 4_Clean_QA Review		
Type	Version	Document Identifier	Effective Date	
elido_clinical_doc	1.0; CURRENT; Most-Recent; Effective	090032d580d43d4b	19-May-2017 09:57:58	
Reason For Issue	Auto Issue			

5.7. Rescue Therapy

No rescue therapy is required in this study as the common cold is a self-limiting disease.

5.8. Product Assignment

A unique screening number will identify each subject screened for study participation. Screening numbers will be assigned in ascending numerical order as each subject signs their consent form. Only the assigned screening number should be entered in the field labelled “Subject ID” on the CRF. Once assigned to a subject, a screening number will not be reused.

5.8.1. Randomization

This study will use validated interactive response technology (IRT). The IRT system will be set-up, validated and administered by the CRO in accordance with the Sponsor approved protocol. The randomization schedule and treatment kit schedule will be generated under the responsibility of the CRO and uploaded into the validated IRT system. The randomization schedule will be set up using the method of randomly permuted blocks with a fixed block size.

The IRT system will randomize and stratify by site and by dosing time on Day 1. The maximum number of subjects each site can randomize will be capped at 45 (15% of the target number of randomized subjects). This is to ensure that the study population is reasonably distributed across as many sites as possible, and not dominated by one or two sites providing the majority of subjects. The IRT system will generate an initial shipment and re-supply shipments of numbered treatment kits for each treatment arm to the sites as subjects are enrolled.

All subjects that have signed an Informed Consent Form will be assigned an IRT generated subject number. The site will log into the IRT system and enter the required subject information; the IRT system will then assign a subject number, the subject will then meet the inclusion criteria and be enrolled or not meet inclusion criteria and excluded from the study. Those subjects excluded from the study will be recorded as Screen Failed in the IRT system.

Subjects who meet all inclusion criteria will be assigned by IRT to one of two treatment arms (1146A or placebo) in a 1:1 allocation ratio using the method of randomly permuted blocks with a fixed block size in accordance with the stratified randomization schedule. All site personnel will be blinded to the treatment

Document Name	CCI	Protocol B_Final_Amendment 4_Clean_QA Review		
Type	Version	Document Identifier	Effective Date	
elido_clinical_doc	1.0; CURRENT; Most-Recent; Effective	090032d580d43d4b	19-May-2017 09:57:58	
Reason For Issue	Auto Issue			

allocations. Sponsor and CRO personnel who may influence study outcomes are kept blinded to the treatment allocations.

When a treatment arm is assigned to a subject, the IRT system will assign a randomization number to the subject and a treatment kit from the assigned arm that was previously allocated by the IRT system and shipped to the site. The treatment kit the IRT system assigns to the subject will then be dispensed to the subject. The site will enter the IRT generated subject number, randomization number and treatment kit number into the sites log.

If a subject fails to be randomized for any reason, the subject number and the reason for not being randomized will be entered in the sites log.

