	elde_clinical_doc	1.0: CURRENT: Most-Recent: Effective				090032d580d43d4b	19 May 2017 09:57:58
	Reason For Issue	Auto Issue					

				Assessment of Common Cold Signs & Symptoms by Subjects	
Amendment No.: 4	Non-Substantial/Minor 	1. Sample size has been lowered due to recent awareness of publications with studies employing the use of products with similar purported mechanisms of actions 2. Clarification that freezer temperatures can be below -70°C	Informed Consent  Yes  No Safety Statement  Yes  No CRF  Yes  No	1. Protocol Synopsis, Section 3.1 Study Design, Section 3.3 Type and Planned Number of Subjects, Section 9.1 Sample Size Determination, Section 11 References 2. Section 6.2.3 Nasal Swab Sample	Signature: PPD
Protocol Version No.: 5.0	Substantial/ Major 				Date: PPD

Document Name	CCI	Protocol B_Final_Amendment 4_Clean_QA Review		
Type	Version	Document Identifier	Effective Date	
elido_clinical_doc	1.0; CURRENT; Most-Recent; Effective	090032d580d43d4b	19-May-2017 09:57:58	
Reason For Issue	Auto Issue			

SCHEDULE OF EVENTS

PROCEDURE	VISIT 1 (Day 1)		AT HOME PROCEDURES (Days 2-7)	VISIT 2 (Day 8) ^a
	Screening	Treatment Phase		End of study or early termination
Written informed consent	X			
Demographic data	X			
Medical history	X			
Record prior & concomitant medications and non-drug treatments/ procedures	X	X	X	X
Common cold symptom assessment ^b	X			
Vital signs ^c	X			X
Physical examination	X			X
Nasal examination	X			X
Urine drug screen	X			
Urine pregnancy test ^d	X			X
Inclusion/exclusion criteria	X			
RANDOMIZATION ^e	X			
Dispense & train subjects on e-diary		X		
Self-assessment of common cold symptoms in subject e-diary ^f		X	X	X
Nasal swab sample ^g		X		
Instruct subjects on proper use of study treatment ^h		X		
Dispense & prime 1 st study device		X		
Study treatment administration ⁱ		X	X	
Collect subject e-diary				X
SAE and AE assessment and recording ^j	X	X	X	X
Study conclusion ^k				X

^a Subjects who discontinue study treatment before completing the study and those who prematurely withdraw from the study for any reason should undergo end of study visit procedures in-clinic as soon as possible.

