9.1 Sample Size Determination

There is no previous experience and data with 1146A in the common cold setting and literature on products similar to 1146A and their efficacy on common cold symptoms is sparse. ~~However, one paper was considered useful to be taken as basis for the sample size estimation. In a previous study (Hull et al, 2007), a nasal irrigation spray, designed to deliver a low pH gel to the nasal cavity was compared to placebo. That study had a comparable scenario in terms of the form (spray) of the study product and regarding the endpoint as the current study. That study measured the cold severity for the 7 days of dosing, defined as the mean of the average of total symptom severity scores at 9:00 across the 7 days of dosing and of average of total symptom severity scores at 21:00 across the 7 days of dosing. The total symptom severity score was calculated per assessment by summing the severity scores across the 5 symptoms sore/scratchy throat, runny nose, blocked nose, cough, and tired/run down feeling (each scored using a 4 point scale 0 = absent, 1 = mild, 2 = moderate, and 3 = severe). The mean score of the average of the total symptom severity score reported for placebo was 0.8 with a standard deviation of 0.4 (n = 85). Although the endpoint used in the Hull study differs slightly from the endpoint(s) in the current study and it was calculated over a longer time period (7 days as opposed to 4 days in the current study), it is assumed that the placebo result and the variability reported in the Hull study are indicative for the severity of cold symptoms in such setting and for comparable severity endpoints.~~

UPON REVIEW OF THE MOST RECENT LITERATURE (FAZEKAS ET AL 2012, LUDWIG ET AL 2013 AND ECCLES ET AL 2015), SIMILAR STUDIES EMPLOYING THE USE OF NASAL SPRAY PRODUCTS WITH A SIMILAR PURPORTED MECHANISM OF ACTION HAD SAMPLE SIZES BETWEEN 153 AND 211. THEREFORE, AN APPROXIMATE SAMPLE SIZE OF 170 (85 SUBJECTS IN EACH TREATMENT GROUP) IS CONSIDERED SUFFICIENT FOR THIS STUDY.

A SUFFICIENT NUMBER OF SUBJECTS WILL BE SCREENED TO ENROLL APPROXIMATELY 170 SUBJECTS.

Document Name	CCI	Protocol B_Final_Amendment 4_Clean_QA Review	
Type	Version	Document Identifier	Effective Date
elido_clinical_doc	1.0; CURRENT; Most-Recent; Effective	090032d580d43d4b	19-May-2017 09:57:58
Reason For Issue	Auto Issue		

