~~A sample size of 274 subjects (137 subjects per arm) will achieve 80% power to reject the null hypothesis of equal means in both arms for the average nasal symptom score when the mean difference is 17% (e.g. 0.136 when the placebo mean score result is 0.8) with a common standard deviation of 0.40 and with a significance level (alpha) of 0.05 using a two sided two sample equal variance t test. Considering a dropout rate of approximately 10%, 300 subjects will have to be recruited to have 274 evaluable subjects.~~

~~NQuery Advisor 7.0 Software was used to calculate the sample size.~~

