4.3. Randomization, Stratification, and Blinding

Subjects will be assigned to one of two treatment groups (1146A or placebo) using the method of randomly permuted blocks with a fixed block size in accordance with the stratified randomization schedule. The sites will not receive the randomization schedule, but will be assigned blocks of randomization numbers generated from the IRT system. All site personnel will be blinded to the treatment allocations. GSK and PPD personnel who may influence study outcomes are kept blinded to the treatment allocations.

Subjects who meet all inclusion and exclusion criteria will be randomized to one of the two treatment groups (1146A or placebo) in a 1:1 allocation ratio. The IRT system will randomize and stratify by site and by dosing time on Day 1. The maximum number of subjects each site can randomize will be capped at 26 (15% of the target number of randomised subjects). This is to ensure that the study population is reasonably distributed across as many sites as possible, and not dominated by one or two sites providing the majority of subjects.

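### Protocol 5.8.1 still caps each site at 45 as 15% of the target; against the current target of 170 that is 26.5%, and SAP 4.3 says 26

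*Protocol*

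**What the plan says.** Protocol 5.8.1 (Randomization) limits each site to a number "capped at 45 (15% of the target number of randomized subjects"). It gives the reason in the next sentence: subjects should be spread over many sites and the study "not dominated by one or two sites providing the majority of subjects". The same section says the interactive response technology (IRT) is set up in line with the approved protocol.

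Protocol 9.1 gives the current target: "AN APPROXIMATE SAMPLE SIZE OF 170 (85 SUBJECTS IN EACH TREATMENT GROUP) IS CONSIDERED SUFFICIENT FOR THIS STUDY". The previous basis, under which "300 subjects will have to be recruited to have 274 evaluable subjects", is struck through there.

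The Protocol Amendment Page gives the reason for Amendment 4: "Sample size has been lowered due to recent awareness of publications". The sections it lists as changed for this purpose are "Protocol Synopsis, Section 3.1 Study Design, Section 3.3 Type and Planned Number of Subjects, Section 9.1 Sample Size Determination, Section 11 References". Section 5.8.1 is not among them.

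SAP 4.3 repeats the rule and its purpose with a different number: "capped at 26 (15% of the target number of randomised subjects"). SAP 3.1 and 4.2 both put the target at about 170.

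**The concern.** Section 5.8.1 attaches a percentage to its cap, so the two can be checked against each other, and they no longer agree. The cap appears to have been left behind when the target was cut from 300 to 170.

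Two things are at stake. First, at 45 per site the rule no longer secures its own purpose, since two sites could between them enrol more than half of the trial. The endpoint is self-scored, and center is both a factor in the primary ANCOVA and a stratum in the fallback van Elteren test (SAP 8.1.1), so concentration in two sites bears on how widely the result can be read. Second, the protocol and the SAP state different operating limits. If the IRT follows the protocol, the SAP describes a limit that was not in force.

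**Working it through.** **Inputs**
- Cap in Protocol 5.8.1: 45, described as 15% of target.
- Cap in SAP 4.3: 26, described as 15% of target.
- Current target: about 170 (Protocol 9.1; SAP 3.1 and 4.2).
- Superseded target: 300 (struck-through text in Protocol 9.1).

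**Where 45 comes from.** Cap = 0.15 × target.
- Superseded target: 0.15 × 300 = 45.0, which reproduces the protocol's figure exactly.
- Current target: 0.15 × 170 = 25.5, which does not give 45 but rounds up to the SAP's 26.

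**What each cap allows.** One-site share = cap / target; two-site share = 2 × cap / target; fewest sites that can fill the trial = target / cap, rounded up.

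| Cap and target | One site | Two sites | Fewest sites |
|---|---|---|---|
| 45 of 300 (superseded) | 45/300 = 15.0% | 90/300 = 30.0% | 7 |
| 45 of 170 (Protocol 5.8.1 now) | 45/170 = 26.5% | 90/170 = 52.9% | 4 |
| 26 of 170 (SAP 4.3) | 26/170 = 15.3% | 52/170 = 30.6% | 7 |

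A cap of 26 restores almost exactly the protection of the earlier design.

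**Sensitivity to the approximate target.** Two full sites hold a majority whenever 90/N > 0.5, that is, for any total N below 180. At N = 160 the share is 56.3%, at 175 it is 51.4%, and at 180 exactly 50.0%. Modest over-enrolment beyond 170 therefore does not rescue the figure.

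**Is it a text-extraction artefact?** Where the target was edited, the extracted text runs the deleted 300 and the inserted 170 together. Section 5.8.1 shows 45 alone, with no sign of an edit, and Amendment 4 does not list that section. The 45 is current text.

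**The case against.** The strongest reply is that this is a missed conforming edit with little statistical consequence. Both documents state the same 15% rule, and the SAP has already recalculated it, so the intended limit is easy to recover. Randomization is 1:1 in permuted blocks stratified by site, and center is in the primary model, so unequal site sizes do not bias the treatment comparison. A single site at 45 is 26.5%, not a majority; the purpose fails only if two sites both come close to the cap (43 each gives 86/170 = 50.6%). The documents reviewed give neither the number of sites nor recruitment by site, so the likelihood of that cannot be judged. The IRT setting is also not reported. Finally, the SAP already describes the primary endpoint, demographics and baseline characteristics by center (8.1.1, 6.1, 6.2), so a dominant site would be visible.

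Most of this stands as a limit on the consequence. Bias and type I error are not in question, the two-site majority is something the cap permits rather than a forecast, and the SAP's limit may or may not have been enforced.

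It does not remove the error. A figure in the SAP does not by itself reset a system configured from the protocol. SAP 8.1.1 singles out subjects enrolled after Amendment 3, which suggests enrolment had begun before Amendment 4, when the target was 300 and the cap 45. The system may therefore have been live at 45, and a site may already have passed 26 while complying with the protocol. Describing results by center would reveal concentration but would not prevent it.

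**Conclusion.** The concern holds: the cap in Protocol 5.8.1 is wrong as written. It is 26.5% of the current target rather than the stated 15%, it contradicts SAP 4.3, and it allows two sites to supply 52.9% of subjects. This rests on a target of about 170, and the two-site majority holds for any total below 180. The effect is on site balance, on generalizability and on the agreement between protocol and SAP. Whether any site has in fact exceeded 26, and which cap the IRT applies, cannot be told from the documents. The correction should be made, but it is not a threat to the validity of the primary test.

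**What to change.** Change the cap in Protocol 5.8.1 from 45 to 26, keeping the 15% description, so that it matches SAP 4.3. Confirm in writing which cap the IRT applies and, if it is 45, from what date 26 takes effect.

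If any site has already randomized more than 26, report its count and share in the study report, noting that it complied with the protocol text in force. A sensitivity analysis of the Days 1–4 average nasal symptom score without that site would then be a sensible addition. It is contingent, and the correction does not depend on it: a site with 27 subjects is only 27/170 = 15.9% of the trial, so the analysis is most informative where a site is well above the cap.

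The cost is one number, an IRT settings check, and the recorded justification, approval and IRB handling that the protocol requires for any amendment. Enrolment may slow slightly if a large site reaches 26.
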